TITLE	Randomized controlled study comparing with iASSIST Knee system versus conventional instrumentation
DESIGN	Prospective, comparative, randomized, controlled, multi center
PURPOSE	Determine the effectiveness of the iASSIST Knee in terms of precise implant alignment by comparing iASSIST Knee component alignment with conventional instrumentation
OUTCOME MEASURES	Safety will be assessed by monitoring Adverse Events and Revisions. Clinical outcome will be assessed by monitoring Oxford Knee Score, American Knee Society Score (2011), EQ-5D and Radiographic Assessments.
POPULATION	A multi-center study with a total of 100 subjects (2 groups of 50 subjects) in the Japanese patient population at a maximum of 6 sites.
ELIGIBILITY	Patients will be included according to the locally approved labeling of device in accordance with indications and contraindications for use.
DURATION	Follow-up will take place at 6 months postoperatively. Assuming the enrolment will be completed in 18 months, the total study duration will be 27 months, including central CT assessments.

1. INTRODUCTION

1.1 BACKGROUND

Total Knee Arthroplasty (TKA) is a well-established surgical intervention for patients who suffer from pain and dysfunction due to joint deformation consecutive to degenerative disease such as osteoarthritis and rheumatoid arthritis. Although TKA has been showing excellent clinical results, some early complications have been reported. One identified cause was implant mal-positioning. In order to overcome such alignment issues, implant manufacturers opted to improve the reproducibility of precise osteotomy and other companies have developed computer based technologies such as navigation systems. Navigation systems improved accuracy of implant alignment; however the initial costs and running costs are high. Furthermore, hospitals require sufficient storage space due to the size of certain equipment.

Zimmer Biomet® has developed the *iASSIST Knee* portable intelligent system in order to overcome the cost issues as well as storage space availability while maintaining the advantages of navigation systems. In addition, the accelerometer and gyroscope based *iASSIST Knee* system does not require many steps of pre-operative and intra-operative registration processes.

1.2 DEVICE DESIGN AND DESCRIPTION

The *iASSIST Knee* System is a computer assisted stereotaxic surgical instrument system to assist the surgeon in the positioning of orthopedic implant system components intra-operatively. It involves surgical instruments and position sensors to determine alignment axes in relation to anatomical landmarks and to precisely position alignment instruments and implant components relative to these axes.

iASSIST Knee involves microelectronics instrumented cutting blocks that provide intra-operative verification at each surgical step (bone cuts, overall alignment), thereby reducing mechanical errors. *iASSIST Knee* features simple and intuitive instrumentation based on conventional total knee arthroplasty instrumentation. By eliminating the setup hassles associated with navigation and robotics, *iASSIST Knee* should take less than 2-3 minutes on average to setup, providing a significant cost-effectiveness benefit to patients and surgeons.

The device has been registered in numerous countries across the world for use in routine TKA.

1.3 RATIONALE AND PURPOSE FOR CURRENT STUDY

The purpose of this study is to compare the accuracy of knee component alignment between patients operated with *iASSIST Knee* (Investigational group) versus patients operated without *iASSIST Knee* (Control group) using the same implant system (*Persona*).

2. STUDY DESIGN

The study is a prospective, non-blinded, randomized multi-center study, comparing the use of *iASSIST Knee* versus conventional instrumentation in the hands of experienced surgeons. A total of 100 subjects will be recruited prospectively and randomized according to a 1:1 scheme.

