2.3 PRIMARY AND SECONDARY ENDPOINTS

Primary Endpoint

The primary study endpoint is the alignment accuracy of the knee femoral and tibial components at 6 months for the investigational group compared to the control group.

Secondary Endpoints

- Health Status assessed with the EQ-5D form ⁵
- Operating Room efficiency
 - o OR time
 - o Number of instrument trays used
- Complication rate: incidence of adverse events as well as the proportion of patients who experience at least one complication related to *iASSIST Knee* or conventional instrumentation

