2.5 ASSESSMENT PARAMETERS AND METHODS

Preoperative Data

After the patient has been consented he/she will be assigned randomly to either the investigational or the control group. Historical information will be collected, a detailed medical history will be obtained and a physical examination will be performed (including height and weight). Current medications and smoking history, if applicable, will also be recorded. A baseline OKS, AKSS and EQ-5D will be collected.

Clinical Assessments

OKS and AKSS will be used to assess the difference between the investigational and the control group. This assessment will be completed preoperatively and at 6 months post-operatively.

Patient Questionnaires

EQ-5D⁵ will be taken preoperatively and at 6 months post-operatively.

EQ-5D: Descriptive system of health-related quality of life states consisting of 5 dimensions (mobility, self-care, usual activities, pain/discomfort, anxiety/depression).

Radiographic Assessments

The scan will be performed preferably using the Perth CT protocol (Chauhan et al., 2004). Patient is placed in the supine position with legs rotated into the AP position. The legs should be in maximum tolerable extension. Immobilization sponges may be used as necessary. Allow table movement to cover from ASIS to distal talus. It is preferable that the patient is positioned feet first into the CT gantry. Perform an AP and a lateral scout to cover from ASIS to the mid talus. Scanning parameters will differ according to the CT scanner used and optimal parameters must be standardized based on its own working conditions. Ensure the scan is a low dose scan. Aim to have an effective dose of 2-3 mSv. Helical scan should cover from just above acetabulum to just below ankle joint. FOV should cover both legs. Image reconstruction 2 mm thickness at 1.6 mm interval is desirable. Bone and soft tissue reformats.

Each clinical site sends the scanned image to the independent reviewer with DICOM format after removal of personal information from the image.

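### Patients are not masked and no reason is given, although both arms receive the same implant; EQ-5D and any patient-answered part of OKS, AKSS and complication questioning are open to expectation bias

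*Combined protocol and SAP*

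**What the plan says.** **Blinding.** Section 2 reads: "The study is a prospective, non-blinded, randomized multi-center study, comparing the use of *iASSIST Knee* versus conventional instrumentation". There is no breakdown by role (patient, surgeon, assessor) and no reason for leaving patients unmasked.

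**The contrast.** Sections 1.3 and 2.1 give both arms the Persona implant. Only the instrumentation differs, and Section 1.2 describes iASSIST Knee as an aid used during surgery.

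**Timing of allocation.** Section 2.5 says: "After the patient has been consented he/she will be assigned randomly to either the investigational or the control group". Section 2.4 lists randomization among the preoperative items, ahead of OKS, AKSS and EQ-5D. Section 2.6 allows the preoperative visit up to 3 months before surgery. The sealed envelopes in Section 7.1 conceal the next allocation; they do not keep the arm from the patient afterwards.

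**The outcomes.** Section 2.3 lists as a secondary endpoint: "Health Status assessed with the EQ-5D form". Section 2.5 places EQ-5D under Patient Questionnaires and says it "will be taken preoperatively and at 6 months post-operatively". Under Clinical Assessments the same section says: "OKS and AKSS will be used to assess the difference between the investigational and the control group". OKS and AKSS are not in the Section 2.3 list, but the synopsis says: "Clinical outcome will be assessed by monitoring Oxford Knee Score, American Knee Society Score (2011), EQ-5D and Radiographic Assessments". Complication rate is also a secondary endpoint, and Section 5 has patients questioned about adverse events at each follow-up visit.

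**Testing.** Section 7.3 tests secondary outcomes two-sided at 0.05, without multiplicity adjustment and on complete cases only.

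**The concern.** In EQ-5D the patient is the source of the measurement. A patient who knows at 6 months that a new computer-assisted system was or was not used may answer partly from expectation. The independent CT reviewer gives no protection here, because that reviewer sees only images.

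Many surgical trials cannot mask the patient. Here the implant is the same in both arms, the difference is confined to the operation, and no scheduled assessment requires the patient to know the arm. The plan neither uses that opportunity nor says why it cannot.

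At stake is how a between-arm difference in patient-reported health would be read. If one appeared, it could not be separated from expectation, and a true absence of difference could be reported as a benefit. Because randomization is listed before the baseline forms, knowledge of the arm could reach the baseline scores as well as the 6-month scores.

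**Working it through.** **Plan's own figure.** There is none on this point. The only sample-size calculation concerns the proportion of knees aligned on CT. The plan gives no SD, target difference or expectation effect for EQ-5D, OKS or AKSS, so there is nothing to reproduce.

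**Step 1: can knowledge of the arm reach the answers?**

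| Link in the chain | What the documents give |
|---|---|
| Patient masked? | Declared non-blinded (Section 2); no masking step in 2.4, 2.5, 2.6 or 7.1 |
| Arm assigned when? | Preoperatively, after consent, listed before the baseline forms (2.4, 2.5) |
| Must the patient know the arm? | No scheduled assessment requires it (2.4, 2.6); same implant in both arms (1.3, 2.1) |
| Patient-answered outcomes | EQ-5D clearly (2.5); adverse events partly, by questioning (5); OKS and AKSS not stated |
| Primary endpoint | 6-month CT, images sent to an independent reviewer (2.5, 7) |

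The route to bias is open for EQ-5D and for whatever else the patient answers. It does not run to the CT measurement.

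**Step 2: what would a given shift do?** This is an illustration, because the shift is assumed.

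Inputs from the documents:
- n = 50 per arm (Section 2.1).
- 20% attrition (Section 7, Sample Size), giving 50 × (1 − 0.20) = 40 per arm.
- Two-sided alpha 0.05 (Section 7.3), critical value 1.96.

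Inputs assumed:
- A shift b of 0.1 to 0.4 SD between arms, due to expectation alone.
- No true effect.
- An unadjusted comparison of means, with a normal approximation.

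Formulas:
- SE of the standardised difference = sqrt(2/n).
- P(reject) = 1 − Φ(1.96 − b/SE) + Φ(−1.96 − b/SE).

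For n = 50, SE = sqrt(2/50) = 0.200. For n = 40, SE = sqrt(2/40) = 0.224.

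| Assumed shift b | b/SE, n = 50 | P(reject), n = 50 | b/SE, n = 40 | P(reject), n = 40 |
|---|---|---|---|---|
| 0 | 0 | 5% | 0 | 5% |
| 0.1 SD | 0.50 | 8% | 0.45 | 7% |
| 0.2 SD | 1.00 | 17% | 0.89 | 15% |
| 0.3 SD | 1.50 | 32% | 1.34 | 27% |
| 0.4 SD | 2.00 | 52% | 1.79 | 43% |

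Worked example, n = 50 and b = 0.2: 1 − Φ(0.96) + Φ(−2.96) = 0.169 + 0.002 = 0.170.

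**The case against.** The strongest reply is that this is an ordinary open-label caveat on supportive outcomes. The trial's purpose is component alignment, the only pre-stated conclusion rule concerns alignment on CT, and no success criterion is attached to EQ-5D. This stands as a limit on importance: the main conclusion is not threatened.

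A second reply concerns scope. OKS and AKSS sit under Clinical Assessments, and the plan never says who completes them. A reader might infer that the patient scores both, but the documents do not say so, and neither score is a listed secondary endpoint. On the text alone, EQ-5D carries the point, and OKS and AKSS come in only so far as patients answer them.

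Third, masking may not be achievable. The documents do not describe what patients are told or could learn over 6 months. It is therefore a reasonable inference, not an established fact, that the bias can be avoided. This is a reason to measure how well masking worked and to allow an open-label fallback. It does not explain the absence of any masking step.

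Fourth, leaving allocation until the day of surgery would make it harder for up to 6 sites to have the right instruments ready. That is fair, but masking does not require it: staff can open the envelope earlier and withhold the result from the patient.

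**Conclusion.** The point holds as a risk of bias. Patients are unmasked without a stated reason in a setting where masking looks practicable. The EQ-5D comparison, and any patient-answered part of OKS, AKSS and complication questioning, is exposed to expectation.

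A reader might go further and infer that bias enters every patient-reported comparison, or that it favours iASSIST Knee. The documents support neither: they do not say when or whether patients learn their arm, and neither the size nor the direction of any effect can be derived from them. Nor should 52% be read as the expected error rate. It is the top of an assumed range that runs from about 8% at 0.1 SD with 50 per arm (7% to 43% with 40 per arm), and with no shift the rate stays at 5%.

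This is a cheap improvement to the secondary and clinical outcomes, and it changes nothing in the sample size.

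**What to change.** 1. In Section 2, replace the blanket non-blinded label with surgeon open, patient masked. Say in the consent material that the arm will not be disclosed until the 6-month EQ-5D, OKS and AKSS are complete.
2. In Sections 2.4 and 2.5, have the baseline forms completed before the envelope is opened. Site staff can still open it preoperatively so that instruments can be arranged.
3. At 6 months, have the forms completed before any discussion of the operation or the CT.
4. Add one CRF item at 6 months asking which arm the patient believes they had, and report the answers by arm.
5. Where masking is not feasible, say so with the reason and report these comparisons as open-label.

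**Cost.** Protocol and consent wording, a change in the order of the preoperative steps, and one CRF item. No extra staff, visits or procedures are needed. The continuing burden is that sites must keep the arm out of conversation with the patient for 6 months, and masking may fail in some patients.

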2.1 STUDY GROUPS/TREATMENTS

There will be 2 study groups with each 50 subjects. Patients will be assigned to the investigational or the control group using 1:1 randomization. In the investigational group, patients will be treated with *Persona* and the orientation sensor based device, *iASSIST Knee*. Patients in the control group will have *Persona* TKA with conventional instrumentation.

Group 1 “Investigational”: Patients receiving a *Persona* TKA using *iASSIST Knee*.

Group 2 “Control”: Patients receiving a *Persona* TKA using conventional instrumentation.

2.2 NUMBER OF SITES AND SUBJECTS

A total of 100 subjects will be enrolled and randomly assigned to either the investigational or the control group. This study will be conducted at a maximum 6 Japanese sites.

2.3 PRIMARY AND SECONDARY ENDPOINTS

Primary Endpoint

The primary study endpoint is the alignment accuracy of the knee femoral and tibial components at 6 months for the investigational group compared to the control group.

Secondary Endpoints

- Health Status assessed with the EQ-5D form ⁵
- Operating Room efficiency
 - o OR time
 - o Number of instrument trays used
- Complication rate: incidence of adverse events as well as the proportion of patients who experience at least one complication related to *iASSIST Knee* or conventional instrumentation

2.4 ASSESSMENT PROCEDURE

The study assessment period will be 24 months, 18 months recruitment and 6 months follow-up. The follow-up for all patients will be at the following time points: baseline (preoperative), surgery and 6 months.

A. Preoperative:

- a. Informed consent
- b. Randomization
- c. Enrollment form
- d. Historical record
- e. OKS
- f. AKSS
- g. EQ-5D

B. Operative

- a. Operative Form
 - i. OR time
 - ii. Number of instrument trays used
 - iii. Patella resurfacing (Yes/No)
 - iv. Implanted component information
 - v. Surgical approach

C. 6 months

- a. Limb CT scanning
- b. Complications (if applicable)
- c. OKS

- d. AKSS
- e. EQ-5D

2.5 ASSESSMENT PARAMETERS AND METHODS

Preoperative Data

After the patient has been consented he/she will be assigned randomly to either the investigational or the control group. Historical information will be collected, a detailed medical history will be obtained and a physical examination will be performed (including height and weight). Current medications and smoking history, if applicable, will also be recorded. A baseline OKS, AKSS and EQ-5D will be collected.

Clinical Assessments

OKS and AKSS will be used to assess the difference between the investigational and the control group. This assessment will be completed preoperatively and at 6 months post-operatively.

Patient Questionnaires

EQ-5D⁵ will be taken preoperatively and at 6 months post-operatively.

EQ-5D: Descriptive system of health-related quality of life states consisting of 5 dimensions (mobility, self-care, usual activities, pain/discomfort, anxiety/depression).

Radiographic Assessments

The scan will be performed preferably using the Perth CT protocol (Chauhan et al., 2004). Patient is placed in the supine position with legs rotated into the AP position. The legs should be in maximum tolerable extension. Immobilization sponges may be used as necessary. Allow table movement to cover from ASIS to distal talus. It is preferable that the patient is positioned feet first into the CT gantry. Perform an AP and a lateral scout to cover from ASIS to the mid talus. Scanning parameters will differ according to the CT scanner used and optimal parameters must be standardized based on its own working conditions. Ensure the scan is a low dose scan. Aim to have an effective dose of 2-3 mSv. Helical scan should cover from just above acetabulum to just below ankle joint. FOV should cover both legs. Image reconstruction 2 mm thickness at 1.6 mm interval is desirable. Bone and soft tissue reformats.

Each clinical site sends the scanned image to the independent reviewer with DICOM format after removal of personal information from the image.

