7. STATISTICAL ANALYSIS PLAN

The primary analysis for the study will compare the proportion of alignment accuracy of the knee femoral or tibial components ranging +/- 3 degrees from neutral based on the 6 month postoperative CT scan for *iASSIST Knee* vs. Control (conventional instrumentation).

The primary analysis will test the null hypothesis that the proportion of tibial or femoral component alignment within +/- 3 degrees of neutral for the Investigational group (*iASSIST Knee*) is equal to that of the patients operated without *iASSIST Knee*. The alternative hypothesis is that the proportion of tibial or femoral component alignment within +/- 3 degrees of neutral for the *iASSIST Knee* group is not equal to that of the patients operated without *iASSIST Knee*.

Null Hypothesis: $H_0: \pi_A - \pi_B = 0$

Alternative Hypothesis: $H_A: \pi_A - \pi_B \neq 0$

where π_A represents the proportion of tibial or femoral alignment within +/- 2 degrees from neutral in investigational group on the 6 month postoperative CT scanning and π_B represents the proportion of tibial or femoral alignment within +/- 2 degrees from neutral in control group on the 6 month postoperative CT scanning.

If we reject the null hypothesis, we can conclude that *iASSIST Knee* are more accurate than conventional instrumentation in TKA surgery for either the tibial or femoral component alignment.

Alignment accuracy is defined as the deviation of an angle obtained from the CT scans versus a predefined angle that is accepted for an aligned knee component (refer to the Table 1). Intraoperative validation angles will also be used as targets in the *iASSIST Knee* group. A deviation of +/- 3° is considered to be within the accepted range of an aligned knee component, as reported in the literature^{7, 8}. Massé *et al.* have demonstrated 4.8% *iASSIST* and 30.4% conventional outliers of $\pm 2^\circ$ from neutral for the femur varus-valgus angle, 9.5% *iASSIST* and 60.9% conventional outliers of $\pm 2^\circ$ from neutral for the femur flexion-extension, 4.8% *iASSIST* and 30.4% conventional outliers of $\pm 2^\circ$ from neutral for the tibial varus-valgus angle and 28.6%

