7.1 DETAILED DESCRIPTION OF RANDOMIZATION

In this study, patients will be randomized in one of the two treatment arms: *Persona* TKA with *iASSIST Knee* system (Investigational group) or *Persona* TKA with conventional instrumentation (Control group). The randomization scheme is based on equal numbers per group. The randomization will occur via a random number generator (computer) using blocked randomization procedure. The PI or his/her team does not have influence on the randomization scheme. Sealed opaque envelopes, which will be prepared based on predetermined randomization assignment, will be provided to each study site before study initiation.

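### The plan does not mask the CT reviewer to treatment arm in a trial declared non-blinded, and it leaves open whether both arms are scored against the same target angles

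*Combined protocol and SAP*

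**What the plan says.** Section 2 describes the whole trial: "The study is a prospective, non-blinded, randomized multi-center study". It makes no separate statement about whoever assesses the outcome.

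Section 2.3 sets the endpoint: "The primary study endpoint is the alignment accuracy of the knee femoral and tibial components at 6 months". Section 7 says how it is derived: "Alignment accuracy is defined as the deviation of an angle obtained from the CT scans versus a predefined angle", with the targets in Table 1 (90 degrees for both components in the frontal plane; sagittal targets set before surgery). The result is then classed as in or out of range.

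On the reading itself, section 2.5 says: "Each clinical site sends the scanned image to the independent reviewer with DICOM format after removal of personal information from the image". The schedule in section 2.6 lists an independent CT review at 6 months. The synopsis confirms that the reading is central: "the total study duration will be 27 months, including central CT assessments".

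On targets, section 7 adds: "Intraoperative validation angles will also be used as targets in the" iASSIST group. Section 7.3 defines the primary Fisher test by the predefined Table 1 angles and draws no distinction between arms.

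**The concern.** The surgeon cannot be masked in this trial, but the CT reader can. The primary endpoint is an angle read from an image and judged against a hard cut-off, so a few readings near the cut-off can change the in-range proportion. If the reader knows the arm and leans, even unconsciously, toward the expected result, the lean goes straight into the primary comparison. Images come from sites that know the allocation. The only processing the plan requires before transfer is removal of personal information, which serves privacy.

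The validation angles raise a second, distinct issue. Control patients have no such angles. If those targets entered the primary comparison, accuracy would be measured against a different reference in each arm, and the in-range proportions would no longer be like for like.

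**Working it through.** **Step 1: what protects the reading.** Each statement in the plan that might serve as masking, and what it does:

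- Independent reviewer (2.5, 2.6): concerns who reads, not what the reader knows.
- Central reading (synopsis): one place of reading; says nothing on arm.
- Removal of personal information (2.5): protects patient identity; arm is not mentioned.
- Envelopes (7.1): "Sealed opaque envelopes, which will be prepared based on predetermined randomization assignment, will be provided to each study site before study initiation". These conceal the allocation before assignment and have no bearing on a scan read 6 months after surgery.
- Same implant (1.3): the arms are compared "using the same implant system", so the implant on the image should not reveal the arm. This makes masking feasible but does not establish it.

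No section withholds the arm, operative record or targets from the reader, requires an arm-neutral image code, or locks the readings before they are linked to allocation.

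**Step 2: inputs for an illustration.** The plan gives no figure for reader error, so the size has to be shown under assumptions.

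- From section 7: 70% of controls within 2 degrees; two-sided 5% level; Fisher's exact test; 50 per arm; 20% attrition, so 50 × 0.80 = 40 per arm.
- Cut-off: 3 degrees in the analysis text of sections 7 and 7.3; 2 degrees in the definition of the two proportions and in the sample size. Both are shown.
- Assumed: deviations are normal, centred on target, with the same SD in both arms (no true difference). From 70% within 2 degrees, SD = 2 / 1.036 = 1.93 degrees.
- Assumed: a reading shift of s degrees toward target makes the recorded in-range rate 2Φ((c + s)/SD) − 1 for cut-off c; a shift away from target replaces + s by − s.

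**Step 3: recorded in-range rates at the 3-degree cut-off.**

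- No shift: 2Φ(3/1.93) − 1 = 0.880.
- 0.25 degrees: toward, 2Φ(3.25/1.93) − 1 = 0.908; away, 2Φ(2.75/1.93) − 1 = 0.846.
- 0.5 degrees: toward, 2Φ(3.5/1.93) − 1 = 0.930; away, 2Φ(2.5/1.93) − 1 = 0.805.

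**Step 4: false-positive rate.** This is the exact probability that the two-sided Fisher test rejects, summed over all pairs of binomial outcomes, at 40 / 50 per arm:

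| Reading shift | 3-degree cut-off | 2-degree cut-off |
|---|---|---|
| None | 2.1% / 2.1% | 2.8% / 3.1% |
| iASSIST only, 0.5 toward target | 4.9% / 6.2% | 13.4% / 17.0% |
| Opposing, 0.25 in each arm | 7.3% / 8.5% | 15.3% / 19.8% |
| Opposing, 0.5 in each arm | 27.2% / 33.6% | 56.2% / 68.2% |

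Smaller shifts do little at 3 degrees: iASSIST only by 0.25 degrees gives 2.8% / 3.1%, and opposing shifts of 0.1 degrees give 2.9% / 3.0%.

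**Step 5: the same in counts.** At 50 per arm, 40 v 40 in range gives p = 1.00. If five borderline knees per arm are read in opposite directions, 45 v 35 gives p = 0.023.

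**Step 6: the two target statements.** Section 7 says validation angles are also targets in one arm. Section 7.3 ties the primary test to Table 1 in both arms. The word 'also' can be read as an additional comparison, but nothing says so, and nothing says whether the reader or the statistician subtracts the target.

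**The case against.** The strongest reply is that silence is not exposure. Section 2.5 sends only the image to the reviewer. No section sends the arm, the operative form or the target angles, and section 2.6 lists the operative record and the CT review as separate items. 'Non-blinded' describes the study as a whole. This stands: a reader might infer that the reviewer is told the arm, and the documents do not support that.

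A reader might also infer that the iASSIST-only targets prove the reader is unmasked. They do not. Reading an angle and subtracting a target are separable steps, and a statistician who knows the arm cannot bias an angle already read. Section 7.3 also ties the primary test to Table 1. What remains is a conflict over targets that needs settling in its own right.

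The larger error rates are open to challenge too. The 27.2% / 33.6% result needs opposite biases in both arms, always favouring iASSIST. A constant same-sign error of 0.5 degrees in one arm gives only 2.4% / 2.3% at the 3-degree cut-off. Moving a reading toward target also requires knowing the target, and no section gives the sagittal targets to the reader. Nor do the documents say how angles are extracted from the CT, so the scope for subjective reading is unknown. These points limit the size of the concern; they do not supply the missing masking.

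**Conclusion.** The concern holds as a gap in specification. A team could follow the plan exactly and still have the primary endpoint read with knowledge of the arm, because independence and removal of personal data are the only stated safeguards. It is not shown that the reviewer will be unmasked, or that any bias will occur.

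The possible effect runs from negligible to serious: about 2% to 34% false positives at the 3-degree cut-off in the scenarios tabulated, and more at 2 degrees. This rests on normal deviations with a common SD of 1.93 degrees and on reading shifts whose size and direction are both assumed. The one-arm 0.5-degree case, 4.9% / 6.2% at 3 degrees and 13.4% / 17.0% at 2 degrees, should be reported beside the opposing-shift cases.

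The target question is separate: sections 7 and 7.3 have to agree that both arms are scored against the same reference. Both changes should be made. Neither alters the sample size or the significance level.

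**What to change.** In section 2.5, state that images, including file names and DICOM headers, carry an arm-neutral study code; that the reviewer is masked to arm, operative record and target angles; that the reviewer reports raw component angles only; and that readings are locked before they are linked to allocation.

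In section 7, state that the primary endpoint is the deviation from the same pre-recorded Table 1 target in both arms, computed after the lock by someone other than the reader. Confine the intraoperative validation angles to a separate descriptive analysis within the iASSIST arm.

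The cost is protocol wording and coded file names. The reader is the same, and no extra reads, scans or patients are needed. That the cost is small is a judgement; it rests on the images already being stripped of personal data and read centrally, and on the implant system being common to both arms.
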